- ED nursing staff will be informed about the study during daily huddles in the Emergency Department. Huddles are held three times daily for the nursing staff so that all shifts are informed. CCRC staff will attend the huddles to inform nursing staff of the study and answer any questions. We have utilized this method of education in the past and it is the best way in which to reach all nursing staff. We will attend huddles for the two weeks prior to study start.

ED Pharmacy Staff

ED pharmacy staff will be fully trained on the protocol by [name] and [name]. [name] is a senior pharmacist in the emergency department and is the primary investigator on this study. [name] is a PGY-1 Pharmacy Resident at Regions Hospital and is a Co-Investigator on this study. Both [name] and [name] will participate in training the pharmacy group.

2.7 Describe any interventions that are used in this study.

	Not Applicable
--	----------------

Eligible patients will be randomized in a 1:1 fashion to receive either a fixed dose of 1500 IU or the FDA-approved variable dosing based on body weight and presenting INR. The FDA-approved variable dosing algorithm is as follows: initial INR 2-3.9: 25 IU/kg (maximum dose 2500 IU), initial INR 4-6: 35 IU/kg (maximum dose 3500 IU), and initial INR >6: 50 IU/kg (maximum dose 5000 IU). The patient weight will be obtained using a scale and documented by the treating RN.

Randomization will be initiated with the research team member notifying the attending physician of patient enrollment, and the physician placing the order that is immediately visible in EPIC to the IV pharmacist preparing the medication. The pharmacist will prepare the study medication as either the fixed or variable dose. Exact doses of 4FPCC administered may vary slightly from the calculated doses as the amount of 4FPCC differs based on the vials utilized. The doses are unable to be blinded by the research team, as the fixed dose will have less drug volume.

Following the randomization to study doses, the patient will be monitored for continued bleeding by the treating physician. If the patient receiving the 1500 IU fixed dose remains in a bleeding state and the INR remains above goal, an additional 500 IU may be administered at the physician's discretion to minimize bleeding and attempt to achieve hemostasis. If a

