2.10 Describe your plans for ensuring data security

This study involves only minimum necessary data, in which only de-identified data will be reported. Data will be entered and stored in an HP secure RedCap database. All patients in the RedCap database will be identified only by their assigned study ID number. The database linking the patient MRN and ID number will be stored on a password-protected CCRC share drive that is only accessible to CCRC assigned staff. All electronic identifiers will be destroyed from Regions Hospital computers at the time of manuscript completion. There will not be paper data collection records for this study.

2.11. List the KEY variables that will be collected to support the study aims outlined in item 1.1. KEY variables include those used for:

- 1) achieving the study aims (outcomes, predictors, potential confounders),**
- 2) identifying the study population (for inclusion/exclusion criteria),**
- 3) describing the study population**

Please see an [Example of a Completed Table](#) and an [Example Data Dictionary](#).

Variable Name	Data Source (patient survey, EMR, claims, registry)	Purpose (sample identification, description, grouping variable, study endpoint, predictor, covariate)	Measurement Scale (binary, continuous)
Presenting INR (iSTAT and laboratory value)	EMR	Study endpoint	Continuous
Time of initial INR draw (iSTAT and laboratory value)	EMR	Variable	Continuous
INR at 15 minutes post-administration of 4FPCC	EMR	Study endpoint	Continuous
Dose of 4FPCC in IU	EMR	Study endpoint	Binary
Time to administration of 4FPCC in minutes	EMR	Study endpoint	Continuous
Administration of additional 4FPCC in fixed dose arm	EMR	Study endpoint	Binary
Thromboembolic events within 7 days	EMR	Study endpoint	Binary
Timing of thromboembolic event	EMR	Study endpoint	Continuous

Patient charge of 4FPCC in dollars	EMR	Study endpoint	Continuous
Institution cost of 4FPCC in dollars (cost per unit)	Biocare	Study endpoint	Continuous
Weight (kg) at presentation	EMR	Covariate	Continuous
Use of other reversal agents (vitamin K and FFP)	EMR	Covariate	Binary
Age	EMR	Covariate	Continuous
Indication for 4FPCC	EMR	Covariate	Binary
Attending Provider Specialty (i.e. emergency medicine, trauma, hematology/oncology, neurosurgery)	EMR	Covariate	Binary
Hospital unit (i.e. emergency department, SICU, MICU, etc.)	EMR	Covariate	Binary
Eligible patients not enrolled due to physician discretion	EMR	Covariate	Binary

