****3. ANALYSIS****

3.1 Describe the statistical methods that will be used to address the study aims. For each aim, this will usually include:

- Description of the sample used for the particular analysis
- The variables included in the specific analysis and their role in the analysis
- Numeric summaries computed (e.g., mean, standard deviation, proportion, correlation)
- A summary of data exploration and presentation activities (e.g., generating scatter plots, summary tables)
- Description of statistical tests (e.g., independent samples t-test, Mann-Whitney test), and models constructed (e.g., logistic regression)

Please see our [Examples of Statistical Methods](#).

Describe here:

Note: Please reference the area/pages of an established protocol if you are not writing your own analysis plan.

The analytic study population will consist of patients enrolled during the study period who meet the inclusion/exclusion criteria in Section 2.3 – namely, adults on long-term warfarin therapy who present to the ED with emergent bleeding, or who are in need of urgent invasive surgical procedures. The exposure of interest will be fixed vs. variable dose 4FPCC, to which eligible patients will be randomly assigned in a 1:1 ratio. To evaluate the success of randomization, we will summarize patient demographics and relevant clinical factors by 4FPCC dosing assignment group, and conduct appropriate statistical tests (Fisher's exact test for categorical variables; Wilcoxon test for continuous variables) to identify any differences in the distributions of these factors. If there are no significant differences ($p < 0.05$) found, we will assume successful randomization, and subsequent statistical analyses will not additionally account for covariates.

(Primary) Aim 1: Fixed vs. variable dose 4FPCC and anticoagulation reversal

To evaluate whether fixed dose 4FPCC is acceptably comparable to variable dosing with respect to anticoagulation reversal, as defined by a targeted INR of ≤ 1.5 , we will employ an active-controlled non-inferiority approach to analysis of a randomized trial [D'Agostino 2003]. In order to establish non-inferiority of fixed dosing, we will test the following null and alternative hypotheses:

- $H_0: F - V \leq M$ (Variable dosing is superior to fixed)
- $H_1: F - V > M$ (Fixed dosing is not inferior to variable)

where V = variable dosing, F = fixed dosing, and M = the non-inferiority margin.

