Based on previous literature [D'Agostino 2003, Goldstein 2015] and the available study sample, we propose to set the non-inferiority margin M to -0.1. In other words, if the proportion of warfarin reversal among fixed dose patients is no worse than 10% less than the proportion of warfarin reversal among variable dosed patients, then we will reject the null hypothesis (superiority of variable dosing), and consider the fixed dose to be acceptably non-inferior to variable dosing.

Results to be reported for this aim will consist of the proportion of reversal for each group, the risk difference (RD; the proportion of reversal in fixed group minus the proportion of reversal in variable group), and the risk ratio (RR; the proportion of reversal in fixed group divided by the proportion of reversal in variable group), along with 95% confidence intervals and p-values as appropriate. Non-inferiority will be established if the lower bound of the RD is greater than the pre-specified margin M (-0.1). The primary analysis will use an intent to treat (ITT) approach (fixed vs. variable treatment assignment); however, we will also conduct supplemental analyses using an 'as treated' or 'per protocol' (PP) approach, in which we will compare patients' actual received dose (regardless of assignment) with respect to successful reversal of anticoagulation. We expect the PP approach to complement the primary ITT results, and will be informative particularly if there is non-trivial overlap in dosing by assignment group.

(Secondary) Aim 2: Fixed vs. variable dose 4FPCC and thromboembolic events

Study patients will be followed for 7 days post-administration of 4FPCC for thromboembolic events, as defined in Section 2.12. For this outcome, we will calculate and report the risk (proportion of patients experiencing an event in each group), RD, and RR, with 95% confidence intervals and p-values, as described in Aim 1. While we expect the risk of thromboembolic events to be lower in the fixed dose group, due to the limited number of anticipated thromboembolic events in the study population, the study will not specifically be powered to detect statistically significant differences by dosing group.

(Secondary) Aim 3: Fixed vs. variable dose 4FPCC and costs

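### The supplemental analysis for Aim 1 merges as-treated and per-protocol into one non-randomised comparison, so no per-protocol analysis in the randomised arms is defined alongside ITT for the non-inferiority claim

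*Combined protocol and SAP*

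**What the plan says.** Section 3.1, Aim 1, sets a non-inferiority test on the risk difference (fixed minus variable) with margin -0.1. The primary analysis is ITT by assignment. The supplemental analysis is introduced as as-treated or per-protocol, with the single abbreviation PP, and compares patients by "actual received dose (regardless of assignment) with respect to successful reversal of anticoagulation". Its role is given as follows: "We expect the PP approach to complement the primary ITT results". It is thought informative "particularly if there is non-trivial overlap in dosing by assignment group".

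Other places that bear on how patients would be grouped:

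- Section 3.1, opening paragraph: "The exposure of interest will be fixed vs. variable dose 4FPCC". Baseline factors are tested by assignment group, and if nothing is significant "subsequent statistical analyses will not additionally account for covariates".
- Section 2.7: a patient on the fixed dose may be topped up at the physician's discretion. If that patient "remains in a bleeding state and the INR remains above goal, an additional 500 IU may be administered". Such a patient stays in the ITT analysis and counts as a failure of fixed dosing. No other analysis is mentioned there.
- Section 2.7: "Exact doses of 4FPCC administered may vary slightly from the calculated doses", because of vial content.
- Section 2.11: dose in IU is listed as a binary variable, and "Administration of additional 4FPCC in fixed dose arm" is a separate binary variable.
- Section 2.8: the 15-minute INR is step 6, and recording of the extra dose is step 8.

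**The concern.** A per-protocol analysis keeps patients in their randomised arm and removes defined deviations. An as-treated analysis regroups them by what they received. The plan gives both names to the second of these.

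The difference matters in a non-inferiority trial. Deviations that make the arms alike can pull the ITT difference towards zero, which is the direction that supports the claim. A per-protocol analysis is the usual second look. Here its place is taken by a comparison without the protection of randomisation. The baseline check in section 3.1 covers the assigned groups only, so the received-dose groups could be compared unadjusted with no balance check of their own.

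The plan states 22% power for the primary analysis, so ITT will probably be inconclusive. A supplemental result carrying the PP label may then draw more attention than it can bear.

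**Working it through.** **1. The plan's own figure.** Inputs from section 3.8: 24 per arm, reversal 0.77 in both arms, margin 0.10, alpha 0.05.

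- SE = sqrt(2 × 0.77 × 0.23 / 24) = 0.1215, and 0.10 / 0.1215 = 0.823.
- One-sided 0.05: power = Φ(0.823 − 1.645) = 20.6%. Exact enumeration of the Wald rule gives 22.0%, which reproduces the stated 22%.
- One-sided 0.025: 12.8% (normal) and 14.4% (exact).

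On either count ITT is unlikely to settle the question. Nothing in this point changes that figure.

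**2. Label against definition.** The definition ignores assignment, so the groups are those of an as-treated analysis. In the available text there is no per-protocol set by assigned arm, no list of qualifying deviations, and no rule for how the supplemental result bears on the conclusion.

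**3. Do the two analyses differ?** They do only if there is selective crossover. The documents give no crossover rate, so every input here is assumed, except that the variable-arm rate is set to 0.77. Suppose 25% of patients are hard to reverse. Reversal is 0.85 (others) and 0.53 (hard) on variable dosing, and 0.75 and 0.43 on fixed.

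- Variable: 0.75 × 0.85 + 0.25 × 0.53 = 0.77. Fixed: 0.75 × 0.75 + 0.25 × 0.43 = 0.67. The true difference is −0.10.
- Let a share s of the hard-to-reverse fixed-arm patients receive variable dosing instead. ITT keeps them in the fixed arm, per-protocol drops them, and as-treated moves them to the variable group.

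| s | ITT | Per-protocol | As-treated |
|---|---|---|---|
| 0 | −0.100 | −0.100 | −0.100 |
| 0.25 | −0.094 | −0.084 | −0.070 |
| 0.50 | −0.088 | −0.066 | −0.039 |
| 1 | −0.075 | −0.020 | +0.028 |

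Worked for s = 0.25: per-protocol fixed rate = (0.5625 + 0.1875 × 0.43) / 0.9375 = 0.686; as-treated variable rate = (0.77 + 0.0625 × 0.53) / 1.0625 = 0.756; difference = −0.070. With no crossover all three agree. In this example as-treated is the most favourable to fixed dosing, and per-protocol is biased too.

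**4. Is received dose defined?** By the section 2.7 algorithm, 25 IU/kg × 60 kg = 1500 IU, the same as the fixed dose. Overlap in IU can therefore occur with full adherence. Sections 2.7, 2.11 and 3.1 lean towards grouping by regimen, while the remark in Aim 1 about overlap in dosing points towards IU.

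**5. Conditional illustration only.** Assume grouping by total IU, with topped-up patients leaving the fixed group and not counted in the other. Aim 1 states no such exclusion. Section 1.3 reports bleeding cessation of 96% and 91% in two 1040 IU fixed-dose cohorts. Applied to 24 patients, that leaves 24 × 0.04 = 0.96 and 24 × 0.09 = 2.16 still bleeding. Assume all of them also have INR above goal and are topped up.

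- Equal true rates: reversals = 24 × 0.77 = 18.48. Expected difference = 18.48 / 23.04 − 0.77 = +0.032, and 18.48 / 21.84 − 0.77 = +0.076.
- Fixed at the margin (0.67 against 0.77): expected failures = 24 × 0.33 = 7.92, so the removed shares are 0.96 / 7.92 = 12% and 2.16 / 7.92 = 27%. The chance that the lower limit of a two-sided 95% Newcombe interval exceeds −0.10 is 2.7% with none removed, 4.2% at 12% and 7.6% at 27%.

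The shift is zero if grouping is by regimen started, if topped-up patients stay as fixed-arm failures, or if dose means that given before the 15-minute INR.

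**The case against.** The best defence is that the plan hides nothing. It uses the term as-treated and says in the same sentence that assignment is disregarded, so the fault is a loose synonym. The analysis is supplemental, has no agreement or rescue rule, and cannot overturn ITT. With one initial dose, a study-specific order and an endpoint at 15 minutes, crossover may be rare. A per-protocol set would not be unbiased either. Low power is already acknowledged in section 3.9. All of this stands and limits the weight of the point. It does not supply the missing analysis in the randomised arms.

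A reader might go further and infer that the plan removes failing fixed-arm patients and so inflates the trial's false-positive rate. The documents do not support that. Aim 1 excludes nobody. Section 2.7 attributes the failure to fixed dosing, section 2.11 codes dose as binary and the extra dose separately, and section 3.1 defines the exposure as fixed against variable. The figures in step 5 of the working describe a rule the plan does not state, and they are not error rates of the primary analysis.

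A reader might also infer that the received-dose comparison is bound to be unadjusted. The covariate rule is tied to a check on the assigned groups, so the text leaves this open.

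**Conclusion.** The point holds as one of definition. The analysis called PP is an as-treated, non-randomised comparison, and the available text defines no per-protocol analysis by assigned arm to accompany ITT. Received dose is not fully defined, because regimens can coincide at 1500 IU and the rule for topped-up patients is stated only beside ITT.

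The primary analysis and its stated 22% power are untouched. The practical size is unknown, since no crossover or top-up rate is given, and may be small. The conditional shift of about +0.03 to +0.08 rests on grouping by total IU, on topped-up patients leaving the fixed group, and on cessation rates from 1040 IU cohorts. It is indicative only. The change should be made, but the point is not grounds for doubting the primary result.

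**What to change.** Revise the supplemental analysis in section 3.1, Aim 1:

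1. Use as-treated and per-protocol as two separate terms.
2. Define per protocol as patients who received their assigned regimen within a stated vial-rounding tolerance, analysed in their randomised arm. Keep variable-arm patients whose calculated dose is near 1500 IU in the variable arm. Keep fixed-arm patients given the additional dose in the fixed arm as failures, as section 2.7 does for ITT.
3. Label any received-dose comparison as treated and exploratory, and group it by regimen started, not by total IU.
4. Describe the per-protocol result as a sensitivity check on ITT.

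This is analysis wording only and does not touch dosing or patient management. The exact dose and the use of the additional dose are already collected (sections 2.8 and 2.11). The cost is that the per-protocol set may be a few patients smaller, and it remains a sensitivity check, not an unbiased estimate.

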Cost outcomes will be assessed for all study patients and compared by dosing assignment. Generalized linear regression models will be constructed to estimate the difference in cost attributable to dosing assignment (β estimate), along with 95% confidence intervals and p-values. Specifications of the statistical models constructed will be dictated by the empirical distribution of cost outcomes, which we anticipate will be non-normal. In this case, the negative binomial distribution or other modeling assumptions may be used as appropriate.

Sample size:

3.2 What is the estimated sample size(s) for the primary study analyses (per group for studies with different arms or comparison groups)?

Preliminary data from Regions Hospital identified 67 patients treated with 4FPCC from January 2015 through May 2016, suggesting that we can expect about 4 eligible patients per month. Thus for a 1-year study we anticipate 48 patients in our study population, with approximately 24 patients in each dosing group. We will request approval to enroll up to 60 patients as more may present to the Emergency Department compared to our historical data.

3.3 The sample size selected was (check all that apply):

	Based on data likely to be available during a specific time period (often based on data available in past periods)
	To conduct one or more specific analyses with adequate statistical power
	To achieve a specified level of precision in one or more key estimates
	Other (explain):

3.4 Explain your choice of the sample size selection you listed above:

Sample size for this study will directly depend on the number of eligible patients on warfarin who present to the ED with bleeding emergencies during the study period.

3.5 Describe your assumptions concerning data available for analysis (e.g. How many subjects will be randomized, possibly lost to follow-up or a procedure? What do you expect for survey response rates, and how much missing data do you expect?). Include information as it pertains to your study (human or animal).

Our primary assumptions regarding available data include: 1) successful enrollment of eligible patients into the study; 2) complete data collection for relevant study variables; and 3) an even distribution of random assignment (1:1).

Missing data should be minimal, as the relevant clinical measures under evaluation are routinely documented in this context.

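### Aim 3 by default compares costs without covariates; prespecified adjustment for the algorithm dose, computable in both arms, would narrow the interval for the saving by about 22–29% if dosing follows the algorithm

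*Combined protocol and SAP*

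**What the plan says.** Section 3.1 (Aim 3) states: "Cost outcomes will be assessed for all study patients and compared by dosing assignment". It continues: "Generalized linear regression models will be constructed to estimate the difference in cost attributable to dosing assignment". Assignment is the only predictor it names. The distribution is left open until the costs are seen, with the negative binomial as one possibility.

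The opening of section 3.1 sets the rule for all aims. Baseline factors are tested between arms and, if none differs at the 5% level, "subsequent statistical analyses will not additionally account for covariates". The default is therefore an unadjusted comparison.

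Other sections supply the ingredients of a strong covariate:

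- Section 2.7, fixed arm: "Eligible patients will be randomized in a 1:1 fashion to receive either a fixed dose of 1500 IU".
- Section 2.7, variable arm: "initial INR 2-3.9: 25 IU/kg (maximum dose 2500 IU), initial INR 4-6: 35 IU/kg (maximum dose 3500 IU), and initial INR >6: 50 IU/kg", capped at 5000 IU in the top band.
- Section 2.7, weight: "The patient weight will be obtained using a scale and documented by the treating RN". This is not limited to one arm.
- Section 2.11 lists "Weight (kg) at presentation" as a covariate, presenting INR from both iSTAT and laboratory, and institution cost per unit.
- Section 3.2 expects "approximately 24 patients in each dosing group".

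**The concern.** Cost per unit makes drug cost proportional to dose. In the fixed arm the dose is nearly constant, apart from an optional extra 500 IU. Almost all the sampling variance of the estimated saving therefore comes from which 24 patients, by weight and INR band, fall in the variable arm. The fixed-arm patients carry the same information about that mix, because their algorithm dose can be worked out, but the default analysis does not use it.

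Section 1.1 asks about savings in dollars, and section 6.3 says the results will influence whether the hospital adopts a fixed-dose protocol. Sample size is set by patient flow (sections 3.3 and 3.4), so the analysis is the available route to a tighter dollar estimate.

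**Working it through.** **Figures in the plan.** No SD, power or precision is stated for Aim 3, so there is no Aim 3 figure to reproduce. The cost figures in section 1.2 give a unit price. Both ends of the range give $2.53 per IU ($2,530/1000 and $17,710/7000); mean cost over mean dose gives $7,236.17/3021 = $2.40. The price cancels from the percentage gain.

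**Formula.** Let S² be the variance of dose in the variable arm, T the variance in the fixed arm, and R² the share of S² explained by the algorithm dose, with 24 patients per arm.

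- Unadjusted variance of the difference: (S² + T)/24.
- Adjusted variance: ((1 − R²)S² + T)/24 + R²S²/48. The last term is over 48 because all patients now inform the weight and INR mix.
- Ratio of standard errors: √(1 − f/2), with f = R²S²/(S² + T).

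| f | Narrowing |
|---|---|
| 1 | 29% |
| 0.95 | 27.5% |
| 0.90 | 26% |
| 0.80 | 22.5% |
| 0.70 | 19% |
| 0.50 | 13% |
| 0.40 | 11% |

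When T is small, S cancels, so the missing dose SD matters little. What matters is how closely delivered doses follow the algorithm.

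**Worked example (assumed inputs).** Weight 85 kg (SD 20) and INR bands 35/30/35% give a mean variable dose near 3030 IU, close to the site's 3021 IU, with S about 1073 IU and R² about 0.96. If 10% of fixed-arm patients receive the extra 500 IU, T = 0.1 × 0.9 × 500² = 22,500.

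- Unadjusted: (1,151,329 + 22,500)/24 = 48,910; SE 221 IU.
- Adjusted: (46,053 + 22,500)/24 + 1,105,276/48 = 2,856 + 23,027 = 25,883; SE 161 IU.
- Ratio: 161/221 = 0.73, or 27% narrower.

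Simulation of this case, which adds 500 IU rounding and 5% vial variation, gave SEs of 228 and 172 IU, or 25% narrower. At $2.53 per IU the 95% half-width falls from 1.96 × 228 × 2.53 = $1,131 to 1.96 × 172 × 2.53 = $853, around a saving of 1488 × 2.53 = $3,765.

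**Range by simulation.**

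- Algorithm followed, extra doses in 0–28% of fixed-arm patients: the sampling SE falls 22–27% and the mean interval width 26–29%. The 28% is 100 − 71.8, from the 1500 IU study in section 1.2.
- 15% of doses off the algorithm: 21–23% if R² stays at 0.83–0.86; 17–18% if the departing doses are unrelated to the patient's own algorithm dose.
- 30% off: 18–20% (R² 0.74–0.78), or 10–11% under the harsher assumption.
- Adjusting for weight alone: only about 3–6%.

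**Variance method.** With an arm-by-algorithm-dose interaction, the ordinary regression SE treats the 48 algorithm doses as fixed and omits the R²S²/48 term. In the example that leaves √2,856 = 53 IU instead of 161 IU. Simulated coverage of nominal 95% intervals, with the algorithm followed:

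| Analysis | Coverage |
|---|---|
| Unadjusted | 93–94% |
| Interaction, ordinary SE | 35–69% |
| Interaction, HC3 SE | 40% and 65% (two scenarios) |
| Interaction, covariate-sampling term added | 94–95% |
| No interaction, HC3 SE | 94–96% |

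**The case against.** The strongest reply is that nothing in the plan is wrong. A comparison by random assignment is unbiased and its interval has close to nominal coverage. In every simulated scenario the saving is at least four standard errors (lowest 830/201 = 4.1), so the answer to the section 1.1 question, whether savings are significant, does not change. All of that stands. A reader might infer that the unadjusted analysis is biased or could give the wrong sign; the documents do not support that.

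A reader might also infer that the plan rules covariates out. It does not: a significant baseline test can bring them in, section 2.11 labels weight a covariate, and the Aim 3 model is left open. That route is data-dependent, though, and never names the algorithm dose.

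Third, it is tempting to say that weight and INR almost fully determine variable-arm cost, so that a gain of a quarter is assured. The documents do not show that. The historical maximum of 7000 IU exceeds the algorithm's 5000 IU cap, so some past doses departed from it or were repeated. The two INR readings may also fall in different bands, and the documents do not say which one sets the dose.

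Finally, adjustment done carelessly is worse than none, as the coverage table shows. This is a reason to name the variance method, not to leave the covariate out.

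**Conclusion.** The point holds as an optional improvement in precision, not as an error. By default Aim 3 leaves unused a covariate that the protocol's own dosing rule supplies for both arms. Using it would narrow the interval for the mean dollar saving by about 22–29% if variable-arm doses follow the algorithm closely, and by about 10–20% if 15–30% depart from it (slightly more in the mildest 15% scenario).

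This rests on an assumed dose distribution and departure rate, on cost proportional to dose, and on a mean difference in dollars. It does not carry over directly to a log-link negative binomial model, which estimates a ratio, or to patient charge if that is not proportional to dose.

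**What to change.** In section 3.1, Aim 3:

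1. Define the algorithm dose for every randomised patient from recorded weight and one named initial INR reading (iSTAT or laboratory), namely the reading that the team states is used for dosing.
2. Include it as a covariate whatever the baseline tests show, as a stated exception to the general covariate rule.
3. Report the adjusted mean difference in dollars with a 95% interval, beside the unadjusted difference.
4. Name the variance method. One option is a linear model without interaction, with HC3 errors. The other is the arm-interaction model standardised over all randomised patients, with an interval that includes the sampling variance of the covariate, by bootstrap of patients within arm or by the added term. Do not use the ordinary or HC3 model SE with the interaction.

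The cost is one derived variable and a little more analysis work. No new data item is needed, but weight must actually be recorded in fixed-arm patients, whose dose does not depend on it. The gain is smaller if doses depart from the algorithm, and the unadjusted result remains available.
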